#### Supportive Analysis

The efficacy analyses of the primary endpoint conducted on the MITT population will be repeated on the MPP and CITT populations.

#### *3.4.2 Secondary Efficacy Endpoints*

Analysis of the secondary efficacy endpoints will be supportive only:

- Overall clinical cure at Visits 2, 3 and 4.
- Mycological cure at Visits 2, 3 and 4.
- Therapeutic cure at Visits 2 and 3.
- Changes in signs/symptoms at Visits 2, 3 and 4.

Changes in each sign/symptom (pruritus, otorrhea, ear fullness and otalgia) and in the overall clinical outcome (TSSS) will be analyzed as:

- 2-level approach: resolved/not resolved.
- 3-level approach: resolved/improved/not improved

- mean change in rating from the baseline assessment

The proportion of patients with clinical, mycological and therapeutic cure, the 2-level approach for changes in sign/symptoms and the overall clinical outcome (including the change from baseline and the change from the previous visit) will be summarized by visit and treatment group. For each visit, the proportions of patients will be compared between the treatment groups by using a chi-square test, under a two-sided 5% significance level. The 95% confidence intervals together with the p-value based on the normal approximation to the binomial distribution will be presented for the between-treatment group differences. For each treatment group, the 95% confidence intervals using the Clopper-Pearson method will also be presented.

For Visits 2, 3 and 4, the proportion of patients with a response of Resolved and Not Improved will be compared between the treatment groups by using a chi-square test, under a two-sided 5% significance level. The 95% confidence intervals together with the p-value based on the normal approximation to the binomial distribution will be presented for the between-treatment group differences. For each treatment group, the 95% confidence intervals using the Clopper-Pearson method will also be presented.

Patients with missing efficacy data or indeterminate outcomes will be considered as treatment failures for efficacy analyses. Patients who discontinue for lack of efficacy or rescue medication will be considered as treatment failures.

The statistical analysis of the secondary endpoint will be performed in the MITT population and repeated on the MPP and CITT populations.

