7.2.1 Adverse Events

7.2.1.1 Definitions

An AE is any untoward medical event that occurs in a patient or subject who has received an investigational product, whether or not considered drug related. An AE can therefore be any unfavorable and unintended sign (including abnormal laboratory finding), symptom, or disease temporally associated with the use of an investigational product, whether or not related to the study product.

An illness present at entry to the study is considered a pre-existing condition and will not be considered an AE. However, if a pre-existing condition worsens during the study, this may be considered an AE. Pre-existing conditions will be documented in the EDC. If pre-existing signs and signs/symptoms of otomycosis (pruritus, otalgia, ear fullness and otorrhea) worsen during the study, this will be considered a treatment failure instead of an AE. All AEs, including intercurrent illnesses, that occur during the study (i.e., between Informed Consent Form (ICF) signature and Visit 4) must be reported and documented as described below.

7.2.1.2 *Timing*

Adverse events will be assessed from the time the subject provides informed consent.

Serious adverse events should be collected for up to 30 days after the last dose of study medication.

At study termination, subjects with ongoing AEs/SAEs should be followed up by the Investigator for as long as medically indicated. The Sponsor retains the right to request additional information for any subject with ongoing AEs/SAEs at the end of the study, if judged necessary.

7.2.1.3 *Recording Adverse Events*

Volunteered, observed, and elicited AEs will be recorded. This includes AEs the patient reports spontaneously, those the Investigator observes, and those elicited in response to questions from the study staff. Patients will be asked open-ended questions, such as "How have you been feeling since your last visit?", at each study visit. If a patient reports any pain or illness during or after administration of the eardrops (i.e. itching), the pain or illness experienced by the patient should be recorded as an AE.

All AEs that occur during the study must be recorded in the Adverse Events page of the EDC. All Adverse Event EDC entries should contain a brief description of the event, date and time of onset, duration, intensity, treatment required, relationship to study medication, action taken with regard to study medication, outcome, and whether the event is classified as serious.

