#### 2.3.1.1.5 Overall Clinical Outcome

Overall Clinical Outcome is based on the TSSS, which is calculated by the sum of pruritus score + oinalgia score + ear fullness score + otorrhea score. Patients will be allocated to one of the following categories for Overall Clinical Outcome:

1. Clinical Cure: TSSS is 0, as defined in Sections 2.3.1.1, 2.3.1.2, 2.3.1.3 and 2.3.1.4.
2. Clinical Improvement: TSSS is different than 0 but lower than the previous visit, as defined in Sections 2.3.1.1, 2.3.1.2, 2.3.1.3 and 2.3.1.4.

3. Clinical Failure: TSSS does not meet the definitions of Clinical Cure or Clinical Improvement, as defined in Sections 2.3.1.1.1, 2.3.1.1.2, 2.3.1.1.3 and 2.3.1.1.4.
4. Not changed: TSSS is different than 0 but unchanged compared to the previous visit.
5. Indeterminate: Discontinued (for reasons other than Clinical Failure) or lost to follow up.
6. Not applicable: In case of the non-evaluable ear in patients with unilateral otomycosis or at Visit 2 a new occurrence of otomycosis is determined in the non-evaluable ear and the unilateral otomycosis becomes bilateral.

Patients who take rescue medication (as defined in Protocol Section 6.7.2) will be considered Clinical Failures.

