#### 2.3.2.1 Adverse Events

Adverse events will be recorded throughout the study and at early termination, and will be coded using the Medical Dictionary for Regulatory Activities (MedDRA).

An AE is any untoward medical event that occurs in a patient or subject who has received an investigational product, whether or not considered drug related. An AE can therefore be any unfavorable and unintended sign (including abnormal laboratory finding), symptom, or disease temporally associated with the use of an investigational product, whether or not related to the study product.

An illness present at entry to the study is considered a pre-existing condition and will not be considered an AE. However, if a pre-existing condition worsens during the study, this may be considered an AE. Pre-existing conditions will be documented in the Electronic Data Capture (EDC). If pre-existing signs and signs/symptoms of otomycosis (pruritus, otalgia, ear fullness and otorrhea) worsen during the study, this will be considered a treatment failure instead of an AE.

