### 3.4.2.2 *Changes in signs/symptoms*

Counts and percentages of patients with signs/symptoms (pruritus, otalgia, ear fullness and otorrhea) assessed by the investigator as “Absent”, “Mild”, “Moderate” or “Severe” will be summarized at V1, V2, V3, and V4.

The change from V1 in each sign and symptom will be assessed and classified as follows:

- “Resolved” at V2, V3 and V4 if that sign/symptom is assessed by the investigator as “Absent”
- “Improved” at V2, V3 and V4 if that sign/symptom is assessed by the investigator as:
  - “Mild” and was assessed as “Severe” or “Moderate” at V1 or
  - “Moderate” and was assessed as “Severe” at V1.
- “Remain Absent” at V2, V3 and V4 if the eardrum edema is assessed by the investigator as “Absent” and was assessed as “Absent” at V1
- “Not improved” otherwise

Counts and percentages of patients with a change from V1 in each sign/symptom considered as “Resolved”, “Improved” or “Not improved” will be summarized at V2, V3 and V4 and will be compared between treatment groups by using a chi-square test, under a two-sided 5% significance level. The 95% confidence intervals together with the p-value based on the normal approximation to the binomial distribution will be presented for the between-treatment group differences. For each treatment group, the 95% confidence intervals using the Clopper-Pearson method will also be presented.

Counts and percentages of patients with each sign/symptom considered as “Resolved” or “Not resolved” will be summarized at V2, V3, and V4 and will be compared between treatment groups by using a chi-square test, under a two-sided 5% significance level. The 95% confidence intervals together with the p-value based on the normal approximation to the binomial distribution will be presented for the between-treatment group differences. For each treatment group, the 95% confidence intervals using the Clopper-Pearson method will also be presented.

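### The two AE rules conflict for drop reactions in an ear symptom already present at baseline, and no planned table counts worsening of a single symptom by arm

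*SAP*

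**What the plan says.** **AE rules.** SAP 2.3.2.1 and Protocol 7.2.1.1 say that if pre-existing pruritus, otalgia, ear fullness or otorrhea should "worsen during the study, this will be considered a treatment failure instead of an AE". Protocol 7.2.1.3 has a second rule, which begins "If a patient reports any pain or illness during or after administration of the eardrops (i.e. itching" and directs that the event be recorded as an AE. It makes no exception for symptoms present at baseline. The SAP repeats only the first rule.

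**Individual symptoms.** SAP 3.4.2 plans a resolved/not resolved split, a "3-level approach: resolved/improved/not improved", and the mean change from baseline. SAP 3.4.2.2 defines *Not improved* as whatever is left over. It plans "Counts and percentages of patients with a change from V1 in each sign/symptom considered as" one of those three classes, plus severity counts at each visit. SAP 3.1.2 adds median, SD, minimum and maximum for continuous data. On missing data, SAP 3.4.2 says: "Patients with missing efficacy data or indeterminate outcomes will be considered as treatment failures for efficacy analyses".

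**Total score.** In the Protocol synopsis (Study Evaluation, Visits 2 to 4), worsened is one of the Overall Clinical Outcome categories. SAP 2.3.1.1.5 lists "Clinical Failure: TSSS does not meet the definitions of Clinical Cure or Clinical Improvement" and, separately, "Not changed: TSSS is different than 0 but unchanged compared to the previous visit". SAP 3.4.2 summarises this outcome by visit and arm, "including the change from baseline and the change from the previous visit".

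**Safety.** SAP 3.5 covers AEs, physical examination, vital signs and the pregnancy test. It has no symptom-score table. SAP 3.4 restricts the efficacy analyses to the evaluable ear.

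**The concern.** Itching and ear pain are symptoms of otomycosis and also plausible local reactions to ear drops. If a site applies the drop-reaction rule, the event enters the TEAE tables by SOC and PT (SAP 3.5.1). If it applies the pre-existing-symptom rule, the same event leaves the AE comparison and becomes part of an efficacy class that also holds patients who did not change. Two sites could therefore record the same event differently.

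The comparator is saline, so a local reaction to the clotrimazole solution should appear as a difference between arms. Protocol 2.1 cites a study of clotrimazole 1% in PEG 400 in which two patients had burning in the first two days. That was a different setting (perforated eardrums, Q-tip or ear wick), but it makes the question reasonable. Classification also affects care: under Protocol 5.3, a drug-related AE that ends treatment in one ear ends it in both.

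**Working it through.** The plan states no figure on this point, so there is none to reproduce. The check compares the rules and then asks what the planned tables can recover.

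**1. Where the rules meet.**

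| Event | Protocol 7.2.1.1 / SAP 2.3.2.1 | Protocol 7.2.1.3 |
|---|---|---|
| Itching with the drops, absent at Visit 1 | Exclusion does not apply | AE |
| Baseline itching worsens, unrelated to dosing | Treatment failure, not an AE | Does not apply |
| Baseline itching worsens with the drops | Treatment failure, not an AE | AE |

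Only the third row conflicts. Inclusion criterion 3 requires at least two of pruritus, otalgia and ear fullness. At most one of the two can be fullness, so every eligible patient has pruritus or otalgia at Visit 1.

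**2. What the total score shows.** A rise in the total signs/symptoms score (TSSS) is visible in Overall Clinical Outcome, with two blemishes. An unchanged score also meets the wording of Clinical Failure, and rescue users are classed as failures, though SAP 3.3.5 tabulates them separately. A rise in one symptom can still be hidden. Suppose pruritus goes 3 to 0, fullness 2 to 0, otorrhea 1 to 0 and otalgia 1 to 3. TSSS goes from 3+2+1+1 = 7 to 3, and the patient is a Clinical Improvement while ear pain goes from mild to severe.

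I enumerated all 216 eligible Visit 1 score profiles against all 256 follow-up profiles. A symptom present at Visit 1 rises in 33,183 pairs. TSSS falls in 11,424 of these (34%), is unchanged in 4,796 (14%) and rises in 16,963 (51%). These are equal-weight counts of what is possible, not probabilities. The more closely symptoms move together, the rarer the masking.

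**3. What the single-symptom tables show.** Take 100 patients with invented counts. Rows are Visit 1 scores; entries are the numbers at follow-up scores 0/1/2/3.

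| Visit 1 score | Table A | Table B |
|---|---|---|
| 0 (n=10) | 10/0/0/0 | 10/0/0/0 |
| 1 (n=30) | 17/13/0/0 | 2/16/12/0 |
| 2 (n=40) | 6/15/15/4 | 37/3/0/0 |
| 3 (n=20) | 17/0/0/3 | 1/9/3/7 |

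Both tables give:
- follow-up severity counts of 50/28/15/7
- Resolved 50, Improved 15, Not improved 35
- mean change (79 − 170)/100 = −0.91
- sum of squared changes 213, so SD = √[(213 − 91²/100)/99] = 1.15
- median −1, minimum −3, maximum +1

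Table A has 4 worsened patients (2 to 3). Table B has 12 (1 to 2). The planned outputs are identical, so they do not fix the count.

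The spread of 4 to 12 shows only what is possible; the resolution patterns in A and B are odd. If milder symptoms must resolve at least as often as more severe ones, and a symptom absent at Visit 1 stays absent, the same outputs allow exactly 9. Across 105 feasible settings with these severity margins and restrictions, the gap is at most 3 per 100.

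**4. Precision of a direct count.** Assume all 127 and 64 randomised patients are observed. With 19 v 3 worsened, 15.0% − 4.7% = 10.3 points (Newcombe 95% interval 0.6 to 18.1). With 13 v 3 it is 5.5 (−3.7 to 12.7). With 6 v 3 it is 0.0 (−8.6 to 6.1). The counts are assumed. A table of this kind can only be descriptive.

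**The case against.** The best defence is that the rules do not truly conflict. Protocol 7.2.1.1 concerns the course of the disease and 7.2.1.3 is the specific rule for events with the drops. Its example is itching, an entry symptom, which would be an odd choice if baseline itching were excluded. Protocol 5.3 provides for drug-related AEs in one ear, which fits this reading. It is a natural reading, and many sites may adopt it. But the text does not state it, and the SAP carries only the exclusion.

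Other replies also stand in part:
- **Worsening is not hidden altogether.** A reader might infer that no summary shows any worsening. The documents do not support that: the total score has its own categories, and a maximum change above 0 shows that someone in that arm worsened. SD and maximum can signal worsening, but step 3 shows that they do not count it.
- **Early worsening is partly captured.** Under Protocol 4.1, a patient who attends before Day 8 without improvement or worse, and is taken off study drug, has all Visit 2 procedures, including symptom scores.
- **The data exist.** Symptom tables are repeated in all randomised patients (SAP 3.4.2), and individual scores appear in listings. The Safety population by treatment received therefore adds little for patients; the other treated ear is the larger addition.
- **Missing scores.** The failure rule may place them in *Not improved*, but SAP 3.4.2.2 does not say so.

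A reader might also infer that local reactions will be missing from the safety report, or that about a third of worsened symptoms will be masked. Neither follows. The first depends on how sites apply the rules; the second treats an equal-weight count as a rate.

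**Conclusion.** The point holds as an inexpensive local-tolerability improvement of modest priority. The AE rules give no order of precedence for a drop reaction in a symptom present at baseline, and the planned tables do not count worsening of a single symptom by arm. If sites follow the exclusion as written, some local reactions leave the AE comparison with saline and cannot be counted from the symptom tables. Whether and how often this happens is unknown: the documents give no worsening rate, so no size is claimed. No primary or secondary test changes. The conclusion rests on the wording of the two AE rules, on *Not improved* being a residual class, and on severity being tabulated separately at each visit.

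**What to change.** **Main change.** Add to Protocol 7.2.1.1 and SAP 2.3.2.1: *Pain or itching that the patient reports as a reaction to instillation is recorded as an AE even if the symptom was present at baseline.* The cost is one sentence, with the Protocol part handled under Protocol 11.4. If data collection is over, the sentence cannot recover events that were never recorded; the documents do not say whether it is.

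**Supporting change.** In SAP 3.4.2.2, display *Not improved* as *Unchanged* and *Worsened* (score above Visit 1), with missing shown separately. In SAP 3.5, add one per-symptom shift table from Visit 1 to each later visit. Use observed scores in the Safety population by treatment received, with the evaluable and the other treated ear shown separately, and no test. Its Visit 1 rows separate newly appearing symptoms from worsened ones. The scores are already collected for both ears at every visit, so the cost is programming. The SAP covers CLEAR-1 and CLEAR-2, so the change would serve both.

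**Limits.** The table mixes irritation with disease course, and worsening from untreated infection on saline can mask irritation on clotrimazole. Visit 2 (Day 8-10) is the only on-treatment visit, and otalgia is rated for the visit day only. Brief reactions between visits will still depend mainly on AE reporting, which is why the sentence comes first.

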#### *3.4.2.1 Mycological outcome*

The proportion of patients with a response of Eradication or Presumed Eradication at Visit 2, Visit 3 (EOT) and Visit 4 (TOC) will be compared between the Clotrimazole 1% otic solution and the Placebo treatment groups by using a chi-squared test, under a two-sided 5% significance level. The 95% confidence intervals together with the p-value based on the normal approximation to the binomial distribution will be presented for the between-treatment group differences. For each treatment group, the 95% confidence intervals using the Clopper-Pearson method will also be presented.

Mycological outcome will be summarized by treatment group and visit in terms of proportion in each category at each visit.

If a patient took rescue medication prior to Visit 3, the response will be considered a failure at Visit 3. Similarly, if a patient took rescue medication prior to Visit 4, the response will be considered a failure at Visit 4.

Responses will be summarized in terms of a 3-level response. Responses of Eradication or Presumed Eradication will be categorized as favorable. Responses of Persistence, Presumed Persistence, Superinfection, Reinfection, and Recurrence will be categorized as unfavorable. Indeterminate responses will be categorized as indeterminate. The proportion of patients with a favorable response at Visit 2, Visit 3 and Visit 4 will be compared between the Clotrimazole and Placebo treatment groups by using the same chi-squared test as the primary efficacy endpoint.

Mycological outcome will also be presented by pathogen on the MITT population (Candida spp, Aspergillus spp).

### 3.4.2.2 *Changes in signs/symptoms*

Counts and percentages of patients with signs/symptoms (pruritus, otalgia, ear fullness and otorrhea) assessed by the investigator as “Absent”, “Mild”, “Moderate” or “Severe” will be summarized at V1, V2, V3, and V4.

The change from V1 in each sign and symptom will be assessed and classified as follows:

- “Resolved” at V2, V3 and V4 if that sign/symptom is assessed by the investigator as “Absent”
- “Improved” at V2, V3 and V4 if that sign/symptom is assessed by the investigator as:
  - “Mild” and was assessed as “Severe” or “Moderate” at V1 or
  - “Moderate” and was assessed as “Severe” at V1.
- “Remain Absent” at V2, V3 and V4 if the eardrum edema is assessed by the investigator as “Absent” and was assessed as “Absent” at V1
- “Not improved” otherwise

Counts and percentages of patients with a change from V1 in each sign/symptom considered as “Resolved”, “Improved” or “Not improved” will be summarized at V2, V3 and V4 and will be compared between treatment groups by using a chi-square test, under a two-sided 5% significance level. The 95% confidence intervals together with the p-value based on the normal approximation to the binomial distribution will be presented for the between-treatment group differences. For each treatment group, the 95% confidence intervals using the Clopper-Pearson method will also be presented.

Counts and percentages of patients with each sign/symptom considered as “Resolved” or “Not resolved” will be summarized at V2, V3, and V4 and will be compared between treatment groups by using a chi-square test, under a two-sided 5% significance level. The 95% confidence intervals together with the p-value based on the normal approximation to the binomial distribution will be presented for the between-treatment group differences. For each treatment group, the 95% confidence intervals using the Clopper-Pearson method will also be presented.

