5. STUDY POPULATION

5.1 Inclusion Criteria

1. At least 18 years of age at Visit 1 (Day 1, Screening/Baseline).
2. Clinical diagnosis of fungal otitis externa (otomycosis) in one or both ears, where topical treatment is indicated.
3. Presence of at least two of the following symptoms at baseline: of pruritus, otalgia and ear fullness.
4. Presence of debris and/or drainage clinically consistent with fungal infection, i.e. white or black appearance consistent with *Aspergillus* spp. or *Candida* spp.
5. Otorrhea/debris sample for bacterial and mycological cultures.
6. Provide written informed consent.
7. Willing and able to follow all instructions and attend all study visits.
8. Females who are not pregnant, not lactating and are not planning a pregnancy during the study. All females of childbearing potential (those who are not premenstrual, not postmenopausal or not surgically sterile) will be able to participate only if they have a negative urine pregnancy test at baseline (prior to randomization), and if they agree to use adequate birth control methods to prevent pregnancy throughout the study.

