## 2.3 Study Endpoints

### 2.3.1 *Efficacy Parameters*

#### 2.3.1.1 *Clinical Efficacy Parameters*

##### 2.3.1.1.1 *Pruritus*

Pruritus in both ears will be assessed by the investigator at all visits. For consistency, the same individual should perform all the assessments at all visits, if possible. Pruritus will be assessed as:

- Severe (3) if pruritus is marked or intense
- Moderate (2) if pruritus is definitely present
- Mild (1) if pruritus is slight
- Absent (0) if there is complete absence of pruritus

At Visits 2, 3 and 4, pruritus will be considered resolved if the level is 0. Pruritus will be considered improved if the level is lower than the previous pruritus assessment.

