#### 2.3.1.1.4 Otorrhea

Otorrhea in both ears will be assessed by the investigator at all visits. For consistency, the same individual should perform all the assessments at all visits, if possible. Otorrhea will be assessed as:

- Severe (3): copious discharge that prevents visualization of the tympanic membrane unless the fluid is suctioned
- Moderate (2): the anterior sulcus is full, but the tympanic membrane is still clearly visible
- Mild (1): little fluid accumulating in the anterior tympanomeatal sulcus but the tympanic membrane is still visible
- Absent (0) absence of fluid

At Visits 2, 3 and 4, otorrhea will be considered resolved if the level is 0. Otorrhea will be considered improved if the level is lower than the previous otorrhea assessment.

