### 3.1.3 Handling of Dropouts and Missing Data

Patients with missing efficacy data or indeterminate outcomes will be considered as treatment failures for efficacy analyses.

For the primary and secondary endpoints, patients who discontinue for lack of efficacy or rescue medication will be considered as treatment failures.

In cases of missing or incomplete dates (e.g. AE and concomitant medications), the missing component(s) will be assumed as the most conservative value possible. For example, AEs with missing start dates, but with stop dates either overlapping into the treatment period or missing, will be counted as treatment-emergent, taking the worst-case approach. When partial dates are present in the data, both a partial start date and/or a partial stop date will be evaluated to determine whether it can be conclusively established that the AE started prior to the start of study drug or ended prior to the start of study drug. If the above cannot be conclusively established based on the partial and/or present dates, then the AE will be considered as treatment-emergent. Actual data values as they appear in the original electronic Case report form (eCRF) will be presented in the data listings.

Missing values for other variables will not be imputed and only observed values will be used in data analyses and summaries.

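### As written, a sign or symptom that was absent at Visit 1 and stays absent counts as resolved, so the supportive per-symptom comparisons estimate being symptom-free rather than resolution

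*SAP*

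**What the plan says.** SAP 3.4.2.2 opens by announcing a classification of change: "The change from V1 in each sign and symptom will be assessed and classified as follows". Improved is then defined against the Visit 1 grade, but Resolved is not; an investigator grade of absent at the visit is enough. Remain Absent combines absence at the visit with absence at Visit 1, but its visit condition reads "at V2, V3 and V4 if the eardrum edema is assessed by the investigator as" absent. Not improved takes everyone else. Protocol 10.1.10.2.2 has the same four classes and the same stray term.

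The item definitions agree with the Resolved rule. SAP 2.3.1.1.1 has "At Visits 2, 3 and 4, pruritus will be considered resolved if the level is 0", and SAP 2.3.1.1.4 has "At Visits 2, 3 and 4, otorrhea will be considered resolved if the level is 0". Otalgia and ear fullness follow suit, as do the matching protocol sections.

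SAP 3.4.2 lists a "2-level approach: resolved/not resolved" and a 3-level version (resolved, improved, not improved). Neither contains Remain Absent. On the analysis set it says: "The statistical analysis of the secondary endpoint will be performed in the MITT population", repeated in MPP and CITT. Nothing limits a symptom's denominator to patients who had that symptom at Visit 1. SAP section 5, which lists changes from the protocol, does not mention the point.

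**The concern.** A patient who never had otalgia in the evaluable ear has no otalgia to resolve, yet the rule enters that patient as a treatment success for otalgia. The text shows that the authors meant to hold such patients apart, because they wrote a class for absent-then-absent. The class names a sign that is not in this trial's score, so taken literally it can never apply.

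What is at stake is the meaning of the per-symptom results. A table headed resolved, with a chi-square p-value and a confidence interval for the difference, would mix two groups: patients whose symptom cleared and patients who never had it. The planned counts by severity grade at each visit show how many patients were absent at Visit 1, but not how many of those same patients were absent later. On the literal reading, the planned tables therefore do not let a reader separate the two groups.

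**Working it through.** **Inputs.** The plan states no figure for this point: no baseline prevalence per symptom, no stay-absent rate and no per-symptom resolution rate. Its only design figures (SAP 2.2.4) concern the primary endpoint: 100 v 50 evaluable patients, 60% v 30%, 95% power. The normal-approximation power is 94.6%, so that design reproduces. The point does not depend on it; below, those figures serve only as convenient denominators and rates.

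**Step 1. Follow one patient, absent at Visit 1 and absent at Visit 4, through the rules.**

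| Class | Condition at V1 | Condition at visit | Met? | In 2-level test? | In 3-level test? |
|---|---|---|---|---|---|
| Resolved | none | absent | yes | yes | yes |
| Improved | worse grade | mild or moderate | no | no | yes |
| Remain Absent | absent | absent, eardrum edema only | no, as written | no | no |
| Not improved | none | none of the above | no | no | yes |

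Read literally, the patient is Resolved in both tests. If the stray term is read as the symptom in question, the patient meets Resolved and Remain Absent together. No precedence is given, and Remain Absent still has no place in either comparison. Correcting the term alone leaves the 2-level test as it was.

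**Step 2. Can such patients be enrolled?** Yes. Protocol 5.1 asks for "Presence of at least two of the following symptoms at baseline: of pruritus, otalgia and ear fullness", so the third may be absent. It also accepts debris without drainage, while Protocol 7.1.1.4 grades otorrhea as absent when there is no fluid.

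**Step 3. What the comparison estimates.** Let f be the share absent at Visit 1, r the resolution rate among patients with the symptom at Visit 1, and s the share of initially absent patients who count as absent at the visit.

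- Reported rate = (1 − f) × r + f × s
- Reported difference = (1 − f) × (r1 − r2) + f × (s1 − s2)

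**Step 4. Equal f and equal s.** The second term vanishes. For an assumed r1 − r2 of 30 points:

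- f = 10%: 0.9 × 30 = 27 points
- f = 30%: 0.7 × 30 = 21 points
- f = 50%: 0.5 × 30 = 15 points

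For example, with r of 60% v 30%, s = 100% and f = 30%, the reported rates are 0.42 + 0.30 = 72% and 0.21 + 0.30 = 51%, a difference of 21 points.

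**Step 5. Unequal s.** SAP 3.1.3 says: "For the primary and secondary endpoints, patients who discontinue for lack of efficacy or rescue medication will be considered as treatment failures". Missing efficacy data count as failure too. The stay-absent rates may therefore differ by arm. With an assumed 97% v 90%, add f × 7 points: 27 + 0.7 = 27.7, 21 + 2.1 = 23.1 and 15 + 3.5 = 18.5 points. The shrinkage is partly offset.

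**Step 6. What is untouched.** Therapeutic cure and clinical cure depend on the total score being zero. Entry requires two symptoms, so the baseline total score is above zero and the 2-level analysis of that score has no absent-at-baseline patients. Mean change from baseline does not use these classes.

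**The case against.** The strongest reply is that the proportion free of a symptom at a visit, in all MITT patients, is a legitimate randomized comparison, and that keeping a symptom from appearing is a benefit. The item definitions consistently call level 0 resolved. That stands as a defence of the quantity. It does not defend the label, because the section presents itself as change from Visit 1 and sets aside a class for patients who never had the symptom.

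Two further points stand in part. SAP section 6 refers to detailed programming specifications in a separate document, which may state how these patients are handled; what can be shown is the text of the plan, not what was programmed. The evident intent also favours holding these patients apart in the 3-level test, so the defect there exists only on the literal reading. If it were programmed that way, subtracting the 3-level Resolved count from the 2-level one would give the number who remained absent.

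A reader might infer something stronger: that the rule could produce a treatment difference with no resolution effect at all, or hide the shrinkage exactly. The algebra permits both, but the documents do not support either. The failure rules act on the patient, so they also lower resolution among patients who had the symptom. Suppose stay-absent rates of 95% v 80% arise from such failures, and the same failures apply to patients with the symptom. Equal 60% resolution would then need 0.60/0.95 = 63% on clotrimazole and 0.60/0.80 = 75% on placebo among non-failures, so placebo would have to resolve better. Exact cancellation likewise needs rates chosen for the purpose.

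**Conclusion.** The concern holds as a minor one. As written, the 2-level per-symptom comparison, and the 3-level comparison read literally, estimate the symptom-free proportion and not resolution. With equal f and equal stay-absent rates, the reported difference is (1 − f) times the resolution effect; if the stay-absent rates differ by arm, the shrinkage can be partly offset. How large this is in the trial cannot be said, because every f, r and s used here is an assumption.

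Two other readings should be resisted. The two-of-three entry rule might suggest that the absent shares for pruritus, otalgia and ear fullness average at most one third. Protocol 5.1 does not tie the symptoms to the evaluable ear, so that is not a firm limit, and otorrhea has none. Nor does the point reach the trial's conclusion: SAP 3.4.2 calls these analyses supportive only, and the primary endpoint, clinical cure, total score of zero and mean change are unaffected.

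**What to change.** Confine the change to SAP 3.4.2.2, with matching level descriptions in SAP 3.4.2, and to Protocol 10.1.10.2.2, with 10.1.10.2:

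- In Remain Absent, replace the eardrum-edema term with a reference to the sign/symptom being classified.
- Add to Resolved the condition *and was not Absent at V1*, so that the classes no longer overlap.
- Run the per-symptom 2-level and 3-level comparisons in patients who had that symptom in the evaluable ear at Visit 1.
- Tabulate Remain Absent and new onset, by arm, among patients absent at Visit 1.
- If the whole-MITT proportion is wanted, keep it under the label *symptom-free*.

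Leave the item definitions in SAP 2.3.1.1.1 to 2.3.1.1.4 and Protocol 7.1.1.1 to 7.1.1.4 as they are. The definition of Clinical Cure refers to them, and a Visit 1 condition there would touch text behind the primary endpoint for no gain.

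The cost is a few wording edits and one filter on scores already collected. The filter uses a pre-treatment variable, so the arms remain compared as randomized within the subset. The protocol edits follow the route in Protocol 11.4. The real price is smaller denominators: at f = 30%, 100 × 0.7 = 70 v 50 × 0.7 = 35. No power gain is claimed. By exact binomial calculation of the uncorrected chi-square test, with 60% v 30% resolution and f = 30%, the restricted comparison has 83.3% power. The comparison as written has 71.2% if 97% stay absent in both arms and 86.0% at 95% v 80%, so power can move either way. The reason for the change is that the result then matches its label.
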